The incidence of day 200 transplant-related mortality (TRM) will be monitored in all patients. If there is sufficient evidence suggesting that the true incidence of day 200 TRM exceeds 25% on either arm, enrollment on that arm will be suspended and the DSMB will be convened to make recommendations regarding protocol modification. Sufficient evidence will be an observed rate of day 200 TRM that corresponds to a one-sided 80% confidence interval with a lower limit greater than 25%. These limits will be examined after every 5th enrolled patient becomes eligible for evaluation. In practice, the study arm will be suspended if we observe the following number of TRM in study patients: 3/5, 5/10, 6/15, 8/20, 9/25, 10/30, 12/35, 13/40, 15/45 or 16/50 per disease subgroup per study arm (Regimen A versus Regimen B). Table 6 summarizes the operating characteristics of this stopping rule, for enrollment of up to 50 patients per disease subgroup per study arm (Regimen A versus Regimen B) as estimated from 5,000 Monte Carlo simulations. We will apply stopping rules to regimens A and B separately.

The protocol related to regimen B was modified in April 2012. Stopping rules for excess day 200 TRM were met in October 2011 due to 3 deaths occurring in the 5 patients enrolled since the January 2011 protocol modifications (1 due to multi-system organ failure; 1 due to ARDS/diffuse alveolar damage; and 1 due to gram positive sepsis (strep viridans) with multi-system organ failure, questioned possible sinusoidal obstructive syndrome/veno-occlusive disease). All deaths occurred before day 100, with two very early on post-transplant day 1 and day 7. However, the causes of death did not appear to be related to any single part of the regimen. The Data Safety Monitoring Board met and reviewed the data and recommended the following: The revised protocol will allow up to 5 more patients to be enrolled on regimen B before reconvening the DSMB, with each patient enrolled no sooner than 28 days following the date of transplantation (defined as the date of stem cell infusion) of the previous patient. The stopping rules for this arm (Regimen B) were not reset and will continue as stated in the protocol. The next stopping rule would be triggered at 5/10. Therefore, if 2 of the next 5 patients enrolled dies on Regimen B (cord blood), the stopping rule would be triggered and the DSMB will reconvene.

Table 6. Probability of stopping the trial for excess day 200 TRM

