| Number of patients | True rate of event | Probability of stopping |
|--------------------|--------------------|-------------------------|
| 10 | 15% | 0.03 |
| 15 | 15% | 0.04 |
| 20 | 15% | 0.04 |
| 25 | 15% | 0.05 |
| 10 | 35% | 0.32 |
| 15 | 35% | 0.49 |
| 20 | 35% | 0.54 |
| 25 | 35% | 0.63 |
| 10 | 45% | 0.57 |
| 15 | 45% | 0.78 |
| 20 | 45% | 0.84 |
| 25 | 45% | 0.91 |

The incidence of graft rejection will also be monitored in all patients. Regimen A and B will be monitored/analyzed separately. If there is sufficient evidence to suggest that the true incidence of graft rejection exceeds within the first 365 days 10% on either arm, enrollment will be suspended on that arm and the DSMB will be convened to make recommendations regarding protocol modification and/or dose escalation. Sufficient evidence will be an observed rate of graft rejection that corresponds to a one-sided 80% confidence interval with a lower limit greater than 10%. These limits will be examined after every 5th enrolled patient becomes eligible for evaluation. In practice, the study arm will be suspended if we observe the following number of graft rejections in study patients: 2/5, 3/10, 3/15, 4/20, 5/25, 5/30, 6/35, 7/40, 7/45 or 8/50 per disease subgroup per study arm (Regimen A versus Regimen B). Table 7 summarizes the operating characteristics of this stopping rule for enrollment of up to 50 patients per disease subgroup, as estimated from 5,000 Monte Carlo simulations.

Table 7. Probability of stopping the trial for excess graft rejection

| Number of patients | True rate of event | Probability of stopping |
|--------------------|--------------------|-------------------------|
| 10 | 5% | 0.03 |
| 15 | 5% | 0.05 |
| 20 | 5% | 0.05 |
| 25 | 5% | 0.05 |
| 10 | 20% | 0.38 |
| 15 | 20% | 0.62 |
| 20 | 20% | 0.68 |
| 25 | 20% | 0.72 |
| 10 | 30% | 0.67 |
| 15 | 30% | 0.88 |
| 20 | 30% | 0.93 |
| 25 | 30% | 0.95 |

Therefore, **stopping rules** will be imposed for:

Day 200 TRM > 25% (3/5, 5/10, 6/15, 8/20, 9/25, 10/30, 12/35, 13/40, 15/45, 16/50) per disease subgroup per study arm (Regimen A versus Regimen B).

Day 365 Graft rejection (defined as CD3 T cell chimerism < 5%) > 10% (2/5, 3/10, 3/15, 4/20, 5/25, 5/30, 6/35, 7/40, 7/45, 8/50) per disease subgroup per study arm (Regimen A versus Regimen B)

Day 100 Grade III/IV GVHD >15% for Arm A +rATG PBSC grafts 2/5, 3/10, 4/15, 5/20, 6/25, 7/30, 8/35, 9/40, 10/45, or 11/50

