In October/November 2015 Regimen A of the protocol was modified to increase accrual to a minimum of 20 patients for each subgroup of patients (for example, primary immunodeficiency diseases, hemophagocytic disorders, hemoglobinopathies, and marrow failure disorders) who receive Treosulfan, fludarabine, and rabbit ATG. The protocol will continue to accrue until a minimum of 20 patients are in each subgroup, in order to better evaluate the safety and effectiveness of the regimen in each subgroup. There is no limit to the overall accrual to Regimen A as long as the minimum of 20 patients per subgroup has not been reached and each subgroup will continue to accrue until all subgroups reach a minimum of 20 patients. We estimate the overall accrual will be 100-120 patients. Stopping rules for TRM and graft rejection will be applied separately in each disease subgroup of patients who receive Treosulfan, fludarabine, and rabbit ATG conditioning. There are additional patients with nonmalignant diseases that do not fit into one group that have enrolled onto the protocol and will continue to enroll onto the protocol such as metabolic disorders, autoimmune disorders, or other rare nonmalignant diseases. We will continue to enroll these patients but they will not count towards the stopping rules or enrollment since we do not anticipate very many of these patients. However, they will be reviewed by the data safety monitoring board. Accrual to Arm B will continue as before under the same stopping rules.

In March 2017, the protocol was modified to allow the use of both bone marrow and cord blood from the same HLA-matched sibling donor. Specifically, at the discretion of the PI, bone marrow and cord blood cells from the same HLA-matched sibling donor may be used together for transplantation in cases where such cord blood cells were previously stored. The patients enrolled onto the protocol who receive both bone marrow and cord blood from the same HLA-matched sibling donor will be enrolled onto Regimen A of the protocol and analyzed with this group.

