In March 2018, the protocol was modified to prioritize PBSC (Regimen A) as the preferred stem cell source when feasible. This change was made with the goal of improving donor chimerism. PBSC has a higher risk of graft versus host disease; therefore, a stopping rule for grade III-IV GVHD will be added to the protocol – Regimen A only. Since bone marrow will still be allowed on Regimen A, we will apply this stopping rule to PBSC transplants. If there is sufficient evidence to suggest that the true incidence of grade III-IV GVHD at day 100 exceeds 15% (Regimen A), enrollment will be suspended on that arm and the DSMB will be convened to make recommendations regarding protocol modification. The stopping rule would be triggered if 2 of 5, 3 of 10, 4 of 15, 5 of 20, 6 of 25, 7 of 30, 8 of 35, 9 of 40, 10 of 45, or 11 of 50 experience grade III-IV GVHD. This stopping rule will not be by disease subgroup but for all PBSC transplants. The current PBSC transplants on the protocol will be included in this stopping rule.

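### On Regimen A, patients with metabolic, autoimmune or other rare diseases enter no day-200 TRM or graft-rejection count; adding them as one further group under the listed limits is a cheap backstop

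*Combined protocol and SAP*

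**What the plan says.** All of this is in Section 19 unless noted.

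- **Population monitored.** "The incidence of day 200 transplant-related mortality (TRM) will be monitored in all patients". For the second rule: "The incidence of graft rejection will also be monitored in all patients".
- **Criterion.** Enrollment is to be suspended on sufficient evidence that "the true incidence of day 200 TRM exceeds 25% on either arm". The rejection criterion has the same form, with 10% within 365 days. Sufficient evidence is a one-sided 80% lower confidence limit above the threshold, looked at after every fifth evaluable patient.
- **Limits as operated.** The closing list gives "Day 200 TRM > 25% (3/5, 5/10, 6/15, 8/20, 9/25, 10/30, 12/35, 13/40, 15/45, 16/50) per disease subgroup per study arm". The rejection limits (2/5, 3/10, 3/15, 4/20 and on to 8/50) use the same unit.
- **October/November 2015 modification, Regimen A.** "Stopping rules for TRM and graft rejection will be applied separately in each disease subgroup". Four subgroups are named as examples: primary immunodeficiency, hemophagocytic disorders, hemoglobinopathies and marrow failure, each with a minimum of 20 patients. Metabolic, autoimmune and other rare diseases continue to enroll, but "they will not count towards the stopping rules or enrollment since we do not anticipate very many of these patients". The next sentence adds: "However, they will be reviewed by the data safety monitoring board".
- **March 2018 modification.** A grade III–IV GVHD rule covers all Regimen A PBSC transplants regardless of disease, and "The current PBSC transplants on the protocol will be included in this stopping rule".

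**The concern.** The two rules are introduced as covering everyone, yet one class of Regimen A patients is outside both. The only reason given is that few are expected. That is a good reason to leave them out of the 20-per-subgroup accrual goal. It is a weaker reason to leave them out of safety limits that start at 5 patients; Regimen B met its TRM rule at exactly 3 of 5.

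The plan's background does not show these patients to be low risk. In Section 3B, the centre's myeloablative series of metabolic storage disease, osteopetrosis and HLH (n=27) had 37% transplant-related death by day 200, against the 25% threshold. In Section 3A, 4 of 26 (15%) evaluable HLA-identical related graft recipients with Hurler syndrome failed to engraft, against the 10% threshold. Those were older regimens, HLH is counted today, and failure to engraft is not the same as rejection as defined here. The figures serve only to set scenarios.

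At stake is whether an excess confined to this group would produce a defined suspension, or would depend on someone judging that a handful of events is too many.

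**Working it through.** **Inputs.** From Section 19: thresholds of 25% (TRM) and 10% (rejection), the listed limits, looks every 5 patients, and four subgroups of 20. Scenario rates of 37% and 15% come from Sections 3B and 3A. Acceptable rates of 15% TRM and 5% rejection are the lowest rows of Tables 6 and 7. The number of other-disease patients is not stated; 5, 10 and 20 are assumed.

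**1. Reproduce the plan.** Each limit is the smallest k with P(X ≥ k) < 0.20 for X ~ Binomial(n, 0.25) or Binomial(n, 0.10). At n=20 for TRM, P(X ≥ 7) = 0.214 and P(X ≥ 8) = 0.102, so the limit is 8. For rejection, P(X ≥ 3) = 0.323 and P(X ≥ 4) = 0.133, so it is 4. This reproduces all 20 listed TRM and rejection limits.

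An exact look-by-look binomial recursion, removing paths that cross at 5, 10, 15 or 20 patients, gives at n=20:

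| Rule | True rate | Recomputed | Tables 6 and 7 |
|---|---|---|---|
| TRM | 15% / 35% / 45% | 0.041 / 0.545 / 0.830 | 0.04 / 0.54 / 0.84 |
| Rejection | 5% / 20% / 30% | 0.052 / 0.687 / 0.926 | 0.05 / 0.68 / 0.93 |

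All 24 table entries agree to within 0.02.

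**2. The other-disease patients now.** They enter no count, so their chance of reaching a TRM or rejection limit is 0 at any true rate.

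**3. The same patients as one further group.** With 5 patients there is a single look:

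- TRM 37%, limit 3/5: 10(0.37³)(0.63²) + 5(0.37⁴)(0.63) + 0.37⁵ = 0.201 + 0.059 + 0.007 = 0.267.
- Rejection 15%, limit 2/5: 1 − 0.85⁵ − 5(0.15)(0.85⁴) = 1 − 0.444 − 0.392 = 0.165 (unrounded terms).

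The recursion extends this:

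| Patients | TRM 37% | TRM 15% (false) | Rejection 15% | Rejection 5% (false) |
|---|---|---|---|---|
| 4 or fewer | 0 | 0 | 0 | 0 |
| 5 | 0.267 | 0.027 | 0.165 | 0.023 |
| 10 | 0.378 | 0.031 | 0.241 | 0.028 |
| 20 | 0.612 | 0.041 | 0.472 | 0.052 |

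**4. Cost in false suspensions.** With four independent subgroups of 20 at acceptable rates:

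- TRM now: 1 − (1 − 0.041)⁴ = 0.154. With the group added: 1 − 0.846 × (1 − 0.027) = 0.177 at 5 patients, 0.181 at 10 and 0.189 at 20.
- Rejection now: 1 − (1 − 0.052)⁴ = 0.193 (unrounded stop probability). With the group added: 0.211, 0.216 and 0.235.
- Both rules, treated as independent: 1 − 0.846 × 0.807 = 0.318 now, rising to 0.351, 0.358 and 0.380.

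**5. Is a pooled Regimen A limit also needed?** If all four subgroups share an excess, at least one crosses with probability 1 − (1 − 0.545)⁴ = 0.957 at 35% TRM and 1 − (1 − 0.687)⁴ = 0.990 at 20% rejection. Four subgroups each one event below the limit at 20 would total 28/80 deaths or 12/80 rejections with no crossing at that look. But only 0.08% and 0.27% of random orderings of those totals escape every subgroup limit at every look.

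**The case against.** The exclusion is disclosed, with its reason and its substitute, so it is a choice and not an oversight. A reader might infer three stronger things from it, and the documents support none of them.

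- *These patients are unmonitored.* They are not. Section 19 assigns them to the DSMB. Section 17A has the PI reviewing each patient's outcomes continuously. Section 17G requires notice of fatal SAEs within 24 hours, and Section 17H has the Medical Monitor evaluating every SAE.
- *Events in them can never suspend enrollment.* The GVHD rule counts them if they receive PBSC, now the preferred source, and Section 17I recognises suspension by the PI, IRB, IND sponsor or DSMC. The statement holds only for the TRM and rejection limits.
- *The arm-worded criterion is untested throughout, so a pooled limit is needed.* Regimen B is in practice counted as a whole arm (3/5 met, next limit 5/10). On Regimen A the subgroup limits catch nearly every shared excess.

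The scenario rates can also be called pessimistic. Section 3C reports treosulfan-based regimens in 32 children with nonmalignant disease, 9 of them metabolic, with 84% surviving and one early death; Section 3F describes very low TRM in this trial so far. Nothing cited concerns autoimmune disease. With few patients the added group is weak, and the protocol suspends the study arm on a crossing, so two rejections in a mixed group of five could halt all of Regimen A.

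What stands: the backstop is modest, and its suspension must be confined to the group. What does not: expecting few patients is no safety reason for exclusion, and DSMB review without a limit is not the rule that the opening sentences describe.

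**Conclusion.** The concern holds for Regimen A and for the TRM and graft-rejection rules only. Both rules are said to cover all patients, but those with metabolic, autoimmune or other rare diseases cannot reach either limit. Counting them as one group moves the chance of a trigger from 0 to 0.27–0.61 at 37% TRM and to 0.17–0.47 at 15% rejection, for 5 to 20 patients. Below 5 patients it changes nothing.

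Monitoring by disease subgroup is sound and should stay. The arm-level wording is a mismatch with the limits as operated, to be settled by wording and not by a new rule.

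The sizes rest on assumed group sizes and rates, four subgroups of exactly 20, independence between groups and (for the joint figure) between rules, and outcomes known at once although the endpoints are at day 200 and day 365. This is an improvement to consider, not a defect that undermines the trial.

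**What to change.** In the October/November 2015 paragraph of Section 19, replace the exclusion with: *These patients do not count towards the subgroup accrual goals. Together they form one further group (other diseases) under the listed TRM and graft-rejection limits, including those already treated, examined after every 5th evaluable patient. A crossing suspends enrollment of this group and convenes the DSMB.*

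In the TRM and rejection criteria, for Regimen A, change the arm-level phrase to *in any disease group on the arm*. Keep every subgroup limit and add no pooled table. The March 2018 GVHD rule is the precedent for bringing earlier patients into a new count.

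The cost is a few words and one extra row in the DSMB report, on data already collected. The chance of any false suspension rises by about 2 to 4 percentage points per rule, or from about 32% to 35–38% for both rules together. Because the new crossing suspends only the other-diseases group, it does not add to the chance of halting the rest of Regimen A.

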19. STATISTICAL CONSIDERATIONS AND TERMINATION OF STUDY

The primary objective of this clinical trial is to evaluate, within the limits of a phase II study, the preliminary efficacy as defined by engraftment, of a regimen consisting of treosulfan and fludarabine followed by allogeneic HCT in patients with nonmalignant inherited disorders. We plan to enroll at least 30 patients on this study. A minimum of 30 patients will be enrolled onto Arm A. The protocol will continue to accrue until this goal is met. There will be no set limit for Arm B: the cord blood arm. Analyses will be carried out separately between Arm A and B. We will be encouraged to continue study of this treatment if at least 27 of 30 patients engraft. Table 5 shows the probability of observing 27 or more successes among 30 patients for several possible true rates of engraftment.

The protocol was modified in January 2011 and September 2011. Due to a higher than anticipated incidence of acute grade III-IV GVHD for both arms in the first 13 patients (5/13 = 38%; 3/8 bone marrow recipients, 2/5 cord blood recipients) the protocol was modified to add rabbit ATG (thymoglobulin) to both arms initially for unrelated recipients (January 2011) and subsequently for the related recipients (September 2011). In addition, due to graft rejection (n=1) and low donor chimerism/inadequate disease response (n=1) in 2 of the 5 patients enrolled onto the cord blood arm, the cord blood arm was modified to increase the TBI from 200 cGy to 300 cGy TBI for non T-cell deficient patients. The revised protocol will reset the target accrual to at least 30 patients as of January 2011, with a minimum enrollment of 30 onto Regimen A (as stated above). The efficacy analysis will be performed separately for the initial 13 patients (Regimen A: n=8, Regimen B: n=5) and those accrued under the modified regimen. Only patients enrolled after this protocol modification will be counted towards the stopping rules.

Table 5. Probability of observing 27 or more successes in 30 patients

| True rate of engraftment | Pr(\geq 27 successes) |
|--------------------------|--------------------------|
| 70% | 0.01 |
| 80% | 0.12 |
| 90% | 0.65 |
| 95% | 0.94 |

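### Grade III-IV GVHD in marrow and cord recipients counts toward no GVHD limit, although the trial's own early excess arose in those grafts; the event left uncovered is mainly non-fatal grade III

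*Combined protocol and SAP*

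**What the plan says.** All of this is in Section 19 unless another place is named.

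- **The rule.** The March 2018 paragraph adds a limit for Regimen A, to act if there is sufficient evidence that "the true incidence of grade III-IV GVHD at day 100 exceeds 15% (Regimen A") is met. It is confined by graft: "Since bone marrow will still be allowed on Regimen A, we will apply this stopping rule to PBSC transplants". It pools diseases: "This stopping rule will not be by disease subgroup but for all PBSC transplants". A crossing suspends enrolment on the arm and convenes the DSMB.
- **The summary list.** The only GVHD entry is "Day 100 Grade III/IV GVHD >15% for Arm A +rATG PBSC grafts 2/5, 3/10, 4/15, 5/20, 6/25, 7/30, 8/35, 9/40, 10/45, or 11/50". The other two entries, day-200 TRM and day-365 graft rejection, apply to both regimens, per disease subgroup.
- **The early signal.** The January and September 2011 changes were prompted by a "higher than anticipated incidence of acute grade III-IV GVHD for both arms in the first 13 patients (5/13 = 38%; 3/8 bone marrow recipients", with the remaining 2 of 5 in cord recipients. The response was to add rabbit ATG to both arms. The first 13 patients are analysed separately and left out of the stopping rules.
- **The reason for a PBSC rule.** Section 19 says PBSC carries a higher GVHD risk. Section 3F says that no increase over marrow had been seen in this trial, with 10 PBSC recipients.
- **Other cover.** Under Section 17A the DSMB meets twice a year and sees all outcome data. Appendix C gives grades III and IV the same organ stages and separates them by whether the GVHD was fatal.

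**The concern.** The graft groups in which this trial recorded its own grade III-IV excess have no numerical check that the remedy worked. ATG was the response in both arms, and the plan describes no count by which a return of severe GVHD in marrow or cord recipients would trigger a review. The group that has a count is one in which, on ten patients, no increase over marrow had been seen.

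The uncounted groups are not obviously low-risk. Section 6 prefers PBSC for fully matched donors and asks for a discussion with the PI before PBSC is used from a mismatched donor, so mismatched unrelated transplants may tend to use marrow. Regimen B accepts 4/6-matched and double cord units, although its selection algorithm favours single units in order to lower GVHD risk. Regimen B has no accrual limit.

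If grade III GVHD became frequent in these recipients, recognition would depend on judgement at a six-monthly review, with no reference figure.

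**Working it through.** **1. Reproduce the plan's limits.** For TRM and rejection, Section 19 acts when the observed rate has a one-sided 80% lower confidence limit above the reference rate (for rejection, "one-sided 80% confidence interval with a lower limit greater than 10"%). It states no confidence level for GVHD, so I assumed the same one. The exact (Clopper-Pearson) lower limit for x events in n patients is L = the 0.20 quantile of Beta(x, n − x + 1). The limit at each n is the smallest x with L above the reference rate.

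- GVHD, 15%: n = 5, 10, ..., 50 gives 2, 3, 4, 5, 6, 7, 8, 9, 10, 11. All ten match. At n = 5, x = 1 gives L = 0.044 and x = 2 gives 0.169. At n = 10, x = 2 gives 0.083 and x = 3 gives 0.158.
- The same method reproduces all ten TRM limits (25%) and all ten rejection limits (10%).

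**2. Set the early counts against those limits.** The source is "5/13 = 38%; 3/8 bone marrow recipients, 2/5 cord blood recipients".

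| Group | Events | Rate | One-sided 80% lower limit | Two-sided 95% CI |
|---|---|---|---|---|
| Marrow | 3/8 | 37.5% | 19.9% | 8.5 to 75.5% |
| Cord | 2/5 | 40% | 16.9% | 5.3 to 85.3% |
| Both | 5/13 | 38.5% | 24.8% | 13.9 to 68.4% |

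Cord's 2/5 is the PBSC limit at five patients. Three marrow events in eight patients already secure the 3/10 limit. All three lower limits exceed 15%. The evidence is still thin: P(5 or more of 13 at a true 15%) = 0.034.

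**3. Chance of crossing if the same limits covered one more group.** This is an exact sequential binomial with a look after every fifth patient. At each look, take the distribution of the event count among paths that have not yet crossed, add a Binomial(5, p) increment, and move any count at or above the limit to crossed. The first look at p = 0.25 can be checked by hand: 1 − 0.75⁵ − 5(0.25)(0.75⁴) = 1 − 0.237 − 0.396 = 0.367. The same recursion agrees with Tables 6 and 7 to within about 0.01.

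| True rate | By 5 | By 10 | By 20 |
|---|---|---|---|
| 5% | 0.02 | 0.03 | 0.03 |
| 10% | 0.08 | 0.11 | 0.14 |
| 15% | 0.16 | 0.24 | 0.32 |
| 25% | 0.37 | 0.54 | 0.71 |
| 38% | 0.63 | 0.83 | 0.95 |

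As written, a GVHD event in a marrow or cord recipient contributes to such a crossing with probability 0, whatever the true rate.

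**4. Two added groups.** If they are independent, P(at least one crosses by 20 patients each) = 1 − (1 − q)². At a true 10%: 1 − (1 − 0.138)² = 0.26. At 15%: 1 − (1 − 0.316)² = 0.53.

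**5. Does the TRM limit stand in?** Appendix C makes grade III non-fatal, so it adds nothing directly to a TRM count. With an assumed true day-200 TRM of 10%, the same recursion on the TRM limits gives a crossing probability of 0.01 by 30 patients. If TRM stays at that level, this does not change with the frequency of grade III GVHD.

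**The case against.** The strongest reply is that the restriction is deliberate and coherent. The rule arrived with a change that made PBSC the preferred graft, for the stated reason that PBSC carries more GVHD. The early excess belongs to a superseded regimen, and the sponsor acted on it without any numerical limit, so judgement-based oversight worked. Other cover exists too: fatal GVHD by day 200 can enter the TRM limits, the DSMB sees all outcomes twice a year, and a PBSC crossing suspends the arm, which could include Regimen A marrow.

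Much of this stands, and it rules out three stronger readings that a reader might infer:

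- *That about 38% of current marrow and cord recipients develop grade III-IV GVHD.* The documents do not support this. The 13 patients predate ATG and no later rate is given for these groups.
- *That no count at all can pause marrow or cord enrolment.* TRM and rejection limits apply to both regimens, and a PBSC trigger may pause Regimen A.
- *That PBSC recipients need the limit less.* Ten patients compared with marrow cannot show that.

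What does not stand is that the other safeguards close the gap. Grade III is non-fatal by definition. On Regimen A the TRM counts are split by disease subgroup, and patients outside the named subgroups count toward no TRM or rejection limit. The DSMB has no GVHD figure for marrow or cord. A PBSC trigger never counts a marrow event and lies outside Regimen B.

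It is also fair to say that the documents offer no basis for 15% as the reference rate in cord recipients, and that limits this loose produce pauses at acceptable rates. Both points shape the fix.

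**Conclusion.** The point holds in a limited form. The plan has one GVHD limit, and it leaves out the two graft groups with the trial's only reported grade III-IV excess. What goes uncounted is mainly non-fatal grade III GVHD in Regimen A marrow or marrow-plus-sibling-cord recipients and in Regimen B recipients.

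The size is conditional. If the true rate in one such group were 25%, the trial's own limits would call for a review with probability 0.54 by 10 patients and 0.71 by 20. If severe GVHD returned to the pre-ATG level of 38%, the figures would be 0.83 and 0.95. These describe recurrence scenarios and do not estimate present risk.

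The result rests on three assumptions: that the GVHD limits use the exact one-sided 80% method (inferred from the match at all ten looks), that looks fall after every fifth evaluable patient, and that outcomes are independent. The textual gap is certain. Its practical importance depends on a post-ATG rate that the documents do not give. It should be addressed, but it does not undermine the trial.

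**What to change.** Add two lines to the stopping-rule summary in Section 19 for day-100 grade III-IV GVHD, using the existing limits (2/5, 3/10, 4/15, 5/20 and so on):

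1. Regimen A recipients of marrow, or of marrow plus sibling cord, who received rabbit ATG.
2. Regimen B recipients since rabbit ATG was added.

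State the confidence method for the GVHD limits, and give crossing probabilities in the form of Tables 6 and 7. The sponsor and DSMB should confirm whether 15% is the right reference rate for cord. If they choose another rate, the same formula gives the new limits. Counting patients already treated has a precedent, because the March 2018 paragraph includes the existing PBSC transplants.

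The administrative cost is a short amendment and two tallies; grade II-IV acute GVHD is already a secondary objective. The statistical cost per group by 20 patients is a pause probability of 0.03 at a true 5%, 0.14 at 10% and 0.32 at 15%. For at least one of the two groups it is about 0.26 at 10% and 0.53 at 15%. A crossing suspends enrolment and convenes the DSMB; it does not end the trial.

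If the sponsor prefers not to add limits, the least that is needed is a written reason for leaving these grafts out, and a statement of how the DSMB will judge non-fatal grade III GVHD in them.
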